7.1. Testing Procedures

The following tests and test procedures will be performed during the study:

- 1) Hemoglobin A1c (HbA1c) will be tested using a DCA Vantage or similar point-of-care device or local lab
- 2) Pregnancy tests will be performed using a urine or serum pregnancy test

7.2. Questionnaire

The following questionnaire will be completed by each participant after the crossover study period during which the PLGS system was used. The procedures for administration are described in the study procedures manual.

7.2.1. Usability Questionnaire

The System Usability Scale (SUS) is a 10-item questionnaire that measures the overall usability of a system that will be administered to all participants. It is a valid and reliable measure of the perceived usability of a system and is technology-agnostic. The questionnaire presents statements with five response options (anchoring the options from strongly disagree to strongly agree) and asks users to rate their agreement to the statements. User scores are transformed into a composite score, from 0 to 100, and this score is taken as an overall measure of the system's usability; higher scores indicate better perceived usability.

Administration time is approximately 5 minutes.

CHAPTER 8: ADVERSE EVENTS, REPORTING, AND STOPPING RULES

8.1. Definitions

Adverse Event (AE): Any untoward medical occurrence in a study participant, irrespective of the relationship between the adverse event and the device(s) under investigation.

Serious Adverse Event (SAE): Any untoward medical occurrence that:

- Results in death.
- Is life-threatening; (a non-life-threatening event which, had it been more severe, might have become life-threatening, is not necessarily considered a serious adverse event).
- Requires inpatient hospitalization or prolongation of existing hospitalization.
- Results in persistent or significant disability/incapacity or substantial disruption of the ability to conduct normal life functions (sight threatening).
- Is a congenital anomaly or birth defect.
- Is considered a significant medical event by the investigator based on medical judgment (e.g., may jeopardize the participant or may require medical/surgical intervention to prevent one of the outcomes listed above).

Unanticipated Adverse Device Effect (UADE): Any serious adverse effect on health or safety or any life-threatening problem or death caused by, or associated with, a device, if that effect, problem, or death was not previously identified in nature, severity, or degree of incidence in the investigational plan or application (including a supplementary plan or application), or any other unanticipated serious problem associated with a device that relates to the rights, safety, or welfare of participants (21 CFR 812.3(s)).

Adverse Device Effect (ADE): Any untoward medical occurrence in a study participant which the device may have caused or to which the device may have contributed. (Note that an Adverse Event Form is to be completed in addition to a Device Deficiency or Issue Form).

Device Complaints: A device complication or complaint is something that happens to a device or is related to device performance, whereas an adverse event happens to a participant. A device complaint may occur independently from an AE, or along with an AE. An AE may occur without a device complaint or there may be an AE related to a device complaint.

Device Malfunction: Any failure of a device to meet its performance specifications or otherwise perform as intended. Performance specifications include all claims made in the labeling for the device. The intended performance of a device refers to the intended use for which the device is labeled or marketed. (21 CFR 803.3)

8.2. Reportable Adverse Events

For this protocol, a reportable adverse event includes any untoward medical occurrence that meets one of the following criteria:

- 1) A serious adverse event
- 2) An Adverse Device Effect as defined in Section 8.1, unless excluded from reporting in Section 8.3
- 3) An Adverse Event occurring in association with a study procedure
- 4) Hypoglycemia meeting the definition of severe hypoglycemia as defined below
- 5) Diabetic ketoacidosis (DKA) as defined below

857 Hypoglycemia and hyperglycemia not meeting the criteria below will not be recorded as adverse
858 events unless associated with an Adverse Device Effect. Skin reactions from sensor placement are
859 only reportable if severe and/or required treatment.

860
861 Pregnancy occurring during the study will be recorded.
862

863 **8.2.1. Hypoglycemic Events**

864 Hypoglycemia not associated with an Adverse Device Effect is only reportable as an adverse event
865 when the following definition for severe hypoglycemia is met: the event required assistance of another
866 person due to altered consciousness, and required another person to actively administer carbohydrate,
867 glucagon, or other resuscitative actions. This means that the participant was impaired cognitively to the
868 point that he/she was unable to treat himself/herself, was unable to verbalize his/ her needs, was
869 incoherent, disoriented, and/or combative, or experienced seizure or coma. These episodes may be
870 associated with sufficient neuroglycopenia to induce seizure or coma. If plasma glucose measurements
871 are not available during such an event, neurological recovery attributable to the restoration of plasma
872 glucose to normal is considered sufficient evidence that the event was induced by a low plasma
873 glucose concentration.

874 875 **8.2.2. Hyperglycemic Events/Diabetic Ketoacidosis**

876 Hyperglycemia not associated with an Adverse Device Effect is only reportable as an adverse event
877 when one of the following criteria is met: (1) the event involved DKA, as defined by the Diabetes
878 Control and Complications Trial (DCCT) and described below, or (2) in the absence of DKA if
879 evaluation or treatment was obtained at a health care provider facility for an acute event involving
880 hyperglycemia or ketosis.

881
882 Hyperglycemic events are classified as DKA if the following are present:

- 883 • Symptoms such as polyuria, polydipsia, nausea, or vomiting;
- 884 • Serum ketones >1.5 mmol/L or large/moderate urine ketones;
- 885 • Either arterial blood pH <7.30 or venous pH <7.24 or serum bicarbonate <15 ; and
- 886 • Treatment provided in a health care facility

887
888 All reportable Adverse Events whether volunteered by the participant, discovered by study personnel
889 during questioning, or detected through physical examination, laboratory test, or other means will be
890 reported on an adverse event form online. Each adverse event form is reviewed by the Medical
891 Monitor to verify the coding and the reporting that is required.

892 893 **8.2.3. Relationship of Adverse Event to Study Device**

894 The study investigator will assess the relationship of any adverse event to be related or unrelated by
895 determining if there is a reasonable possibility that the adverse event may have been caused by the
896 study device.

897
898 To ensure consistency of adverse event causality assessments, investigators should apply the following
899 general guideline when determining whether an adverse event is related:

900
901 **Yes**

902 There is a plausible temporal relationship between the onset of the adverse event and the study
903 intervention, and the adverse event cannot be readily explained by the participant's clinical state,
904 intercurrent illness, or concomitant therapies; and/or the adverse event follows a known pattern of

905 response to the study intervention; and/or the adverse event abates or resolves upon discontinuation of
906 the study intervention or dose reduction and, if applicable, reappears upon re-challenge.
907

908 **No**

909 Evidence exists that the adverse event has an etiology other than the study intervention (e.g.,
910 preexisting medical condition, underlying disease, intercurrent illness, or concomitant medication);
911 and/or the adverse event has no plausible temporal relationship to study intervention.
912

913 **8.2.4. Intensity of Adverse Event**

914 The intensity of an adverse event will be rated on a three point scale: (1) mild, (2) moderate, or (3)
915 severe. It is emphasized that the term severe is a measure of intensity: thus a severe adverse event is
916 not necessarily serious. For example, itching for several days may be rated as severe, but may not be
917 clinically serious.

- 918 • **MILD:** Usually transient, requires no special treatment, and does not interfere with the
919 participant's daily activities.
- 920 • **MODERATE:** Usually causes a low level of inconvenience or concern to the participant and
921 may interfere with daily activities, but is usually ameliorated by simple therapeutic measures.
- 922 • **SEVERE:** Interrupts a participant's usual daily activities and generally requires systemic drug
923 therapy or other treatment.

924 **8.2.5. Coding of Adverse Events**

925 Adverse events will be coded using the MedDRA dictionary. The Medical Monitor will review the
926 investigator's assessment of causality and may agree or disagree. Both the investigator's and Medical
927 Monitor's assessments will be recorded. The Medical Monitor will have the final say in determining
928 the causality.

929 Adverse events that continue after the participant's discontinuation or completion of the study will be
930 followed until their medical outcome is determined or until no further change in the condition is
931 expected.

932 **8.2.6. Outcome of Adverse Event**

933 The outcome of each reportable adverse event will be classified by the investigator as follows:

- 934 • **RESOLVED** – The participant recovered from the AE/SAE without sequelae. Record the
935 AE/SAE stop date.
- 936 • **RESOLVED WITH SEQUELAE** – The event persisted and had stabilized without change in
937 the event anticipated. Record the AE/SAE stop date.
- 938 • **FATAL** – A fatal outcome is defined as the SAE that resulted in death. Only the event that was
939 the cause of death should be reported as fatal. AEs/SAEs that were ongoing at the time of
940 death; however, were not the cause of death, will be recorded as “resolved” at the time of death.
- 941 • **UNKNOWN** – An unknown outcome is defined as an inability to access the participant or the
942 participant's records to determine the outcome (for example, a participant that was lost to
943 follow-up).
- 944 • **ONGOING** – An ongoing AE/SAE is defined as the event was ongoing with an undetermined
945 outcome.
 - 946 ○ An ongoing outcome will require follow-up by the site in order to determine the final
947 outcome of the AE/SAE.

951 ○ The outcome of an ongoing event at the time of death that was not the cause of death,
952 will be updated and recorded as “resolved” with the date of death recorded as the stop
953 date.

954 All clinically significant abnormalities of clinical laboratory measurements or adverse events occurring
955 during the study and continuing at study termination should be followed by the participant’s physician
956 and evaluated with additional tests (if necessary) until diagnosis of the underlying cause, or resolution.
957 Follow-up information should be recorded on source documents.

958 If any reported adverse events are present when a participant completes the study, or if a participant is
959 withdrawn from the study due to an adverse event, the participant will be contacted for re-evaluation
960 within 2 weeks. If the adverse event has not resolved, additional follow-up will be performed as
961 appropriate. Every effort should be made by the Investigator or delegate to contact the participant until
962 the adverse event has resolved or stabilized.

963 **8.3. Reportable Device Issues**

964 All UADEs, ADEs, device complaints, and device malfunctions will be reported irrespective of
965 whether an adverse event occurred, except in the following circumstances.

966 The following device issues are anticipated and will not be reported on a Device Issue Form but will
967 be reported as an Adverse Event if the criteria for AE reporting described above are met:

- 968 • Component disconnections
- 969 • CGM sensors lasting fewer than 7 days
- 970 • CGM tape adherence issues
- 971 • Pump infusion set occlusion not leading to ketosis
- 972 • Battery lifespan deficiency due to inadequate charging or extensive wireless communication
- 973 • Intermittent device component disconnections/communication failures not leading to system
974 replacement
- 975 • Device issues clearly addressed in the user guide manual that do not require additional
976 troubleshooting
- 977 • Skin reactions from CGM sensor placement or pump infusion set placement that don’t meet
978 criteria for AE reporting

979 **8.4. Pregnancy Reporting**

980 If pregnancy occurs, the participant will be discontinued from the study and a final visit will be
981 conducted. The occurrence of pregnancy will be reported on an AE Form.

982 **8.5. Timing of Event Reporting**

983 Serious or unexpected device-related adverse events must be reported to the Coordinating Center
984 within 24 hours via completion of the online serious adverse event form.

985 Other reportable adverse events and device malfunctions (with or without an adverse event) will be
986 reported within 3 days of the investigator becoming aware of the event by completion of an electronic
987 case report form.

988 Device complaints not associated with device malfunction or an adverse event must be reported within
989 7 days of the investigator becoming aware of the event.

998
999 The Coordinating Center will notify all participating investigators of any adverse event that is serious,
1000 related, and unexpected. Notification will be made within 10 days after the Coordinating Center
1001 becomes aware of the event.
1002
1003 Each principal investigator is responsible for reporting serious study-related adverse events and
1004 abiding by any other reporting requirements specific to his/her Institutional Review Board or Ethics
1005 Committee.
1006
1007 Upon receipt of a UADE report, the Sponsor will investigate the UADE and if indicated, report the
1008 results of the investigation to the sites' IRBs, and the FDA within ten working days of the Sponsor
1009 becoming aware of the UADE per 21CFR 812.46(b) (2). The Medical Monitor must determine if the
1010 UADE presents an unreasonable risk to participants. If so, the Medical Monitor must ensure that all
1011 investigations, or parts of investigations presenting that risk, are terminated as soon as possible but no
1012 later than 5 working days after the Medical Monitor makes this determination and no later than 15
1013 working days after first receipt notice of the UADE.
1014
1015 Device malfunctions will be handled by the Sponsor or designee as described below. In the case of a
1016 CGM transmitter or sensor device malfunction, the Coordinating Center will be contacted and the
1017 Sponsor will be notified accordingly.
1018
1019 **8.6. Stopping Criteria**
1020 **8.6.1. Participant Discontinuation of Study Device**
1021 Rules for discontinuing study device use are described below.
1022
1023 1. The investigator believes it is unsafe for the participant to continue on the intervention. This
1024 could be due to the development of a new medical condition or worsening of an existing
1025 condition; or participant behavior contrary to the indications for use of the device that imposes
1026 on the participant's safety
1027 2. The participant requests that the treatment be stopped
1028 3. Two distinct episodes of DKA
1029 4. Two distinct severe hypoglycemia events as defined in Section 8.2
1030
1031 Even if the study device system is discontinued, the participant will be encouraged to remain in the
1032 study through the final study visit.
1033
1034 Participants who become pregnant will be discontinued from the study with a final clinic visit and no
1035 subsequent use of study device components.
1036
1037 **8.6.2. Criteria for Suspending or Stopping Overall Study**
1038 In the case of a system malfunction resulting in a severe hypoglycemia or severe hyperglycemia event
1039 (as defined in Section 8.2), use of the study device system will be suspended while the problem is
1040 diagnosed.
1041
1042 In addition, study activities could be similarly suspended if the manufacturer of any constituent study
1043 device requires stoppage of device use for safety reasons (e.g. product recall). The affected study
1044 activities may resume if the underlying problem can be corrected by a protocol or system modification
1045 that will not invalidate the results obtained prior to suspension.

1046
1047 The study Medical Monitor will be informed of all serious adverse events and any unanticipated
1048 adverse device events that occur during the study and will review compiled safety data at periodic
1049 intervals. The medical monitor may request suspension of study activities or stoppage of the study if
1050 deemed necessary based on the totality of safety data available.
1051
1052 **8.7. Risks**
1053 The potential risks associated with use of the study device are described in Section 1.4.
1054
1055 Additional risks are minor and/or infrequent and include
1056

- Pain, bruising, redness, or infection from blood draws
- Loss of confidentiality
- Stress from completing quality of life questionnaires
- Skin irritation, infection, or bleeding from CGM sensor or pump infusion set or adhesive
1059 tap
- Breaking of CGM sensor with small portion retained under skin causing redness, swelling,
1060 or pain

1061
1062
1063
1064 The risk of hypoglycemia should be no greater and possibly less than it is in everyday living for
1065 someone with T1D.
1066

CHAPTER 9: MISCELLANEOUS CONSIDERATIONS

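### The 24-hour reporting clock in Protocol 8.5 turns on seriousness or expectedness, while suspension in 8.6.2 turns on event type, so an event that triggers suspension can be due only within 3 days

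*Protocol*

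**What the plan says.** Protocol 8.5 sets two clocks that matter here. The first reads "Serious or unexpected device-related adverse events must be reported to the Coordinating Center", with the limit "within 24 hours via completion of the online serious adverse event form". The second covers the remainder: "Other reportable adverse events and device malfunctions (with or without an adverse event) will be", followed by "reported within 3 days of the investigator becoming aware of the event by completion of an electronic" case report form.

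Protocol 8.6.2 defines the automatic trigger: "In the case of a system malfunction resulting in a severe hypoglycemia or severe hyperglycemia event". It continues "as defined in Section 8.2), use of the study device system will be suspended while the problem is" diagnosed. The safety metrics in 4.4, reused in 5.2 before children aged 6 to 11 may start, are no PLGS-related DKA and no severe hypoglycemia related to system malfunction.

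Protocol 8.2 lists serious adverse events as one reportable category and then lists separately "Hypoglycemia meeting the definition of severe hypoglycemia as defined below", and likewise DKA. On oversight, 8.6.2 states "The study Medical Monitor will be informed of all serious adverse events and any unanticipated" adverse device events. Section 8.2.2 adds that the Medical Monitor reviews each adverse event form, with no deadline.

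**The concern.** The rules that pause the study follow the type of event. The reporting clock follows a site's judgment of seriousness and expectedness. Nothing ties the two together, so an event that should suspend the system can sit on the slower clock.

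The stake is a common-cause fault in the pump or algorithm. The Coordinating Center and Medical Monitor cannot act across sites on an event they do not know about, and other participants, including children from age 6, may be using the same system meanwhile.

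**Working it through.** **Step 1. Set the trigger against the clock.** Take a malfunction that results in severe hypoglycemia, DKA or other reportable hyperglycemia. It is device-related by construction, so the two ways of parsing the 24-hour clause (serious events of any kind, or only device-related ones) make no difference.

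| Site's judgment | Adverse event due (8.5) | On the 8.6.2 Medical Monitor list? |
|---|---|---|
| Serious | 24 hours | Yes |
| Non-serious, unexpected | 24 hours | Only if classed as unanticipated |
| Non-serious, expected | 3 days | No |

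In all three rows the event also fits the 3-day wording for malfunctions with an adverse event, and 8.5 gives no order of precedence. The later sentence in 8.5 on how malfunctions are handled points to text below it that contains no timing.

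**Step 2. Can an event reach the third row?**

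- *Non-serious.* A severe episode reversed at home by a parent meets 8.2.1. It need not meet any limb of the serious adverse event definition in 8.1 except investigator judgment. DKA under 8.2.2 requires treatment in a health care facility, whereas the corresponding limb in 8.1 requires inpatient admission.
- *Expected.* Section 1.4.1 names hyperglycemia as the main device risk. It also foresees ketonemia, and inappropriate suspension when the CGM reads low. Reportable hyperglycemia without DKA is the clearest case.

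So the third row can occur. An event there also falls outside the 10-day notice to other investigators in 8.5, which is limited to events that are serious, related and unexpected.

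**Step 3. Size the difference between the clocks.** The clocks differ by 3 × 24 − 24 = 48 hours, or 2 days. This assumes that both run from investigator awareness; 8.5 says so only for the 3-day clock.

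The inputs come from the projection table in SAP 11: 45 participants have completed at least one week of Period 1, and 22 of them have completed Period 1. Randomization is 1:1.

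- Still in Period 1: 45 − 22 = 23, of whom about 11 to 12 are on PLGS.
- Finished Period 1: 22, of whom about 11 were control-first and are now on PLGS, assuming prompt crossover.
- Concurrent PLGS users: about 22 to 23, leaving out participants in their first week of Period 1.
- PLGS participant-days before a 3-day report is due: 3 × 22 = 66 to 3 × 23 = 69.
- Before a 24-hour report is due: 22 to 23.
- Difference: 66 − 22 = 44 to 69 − 23 = 46.

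The SAP calls this projection rough. If 10 to 50 people were on PLGS at once (an assumption, not a figure in the documents), the difference would be 2 × 10 = 20 to 2 × 50 = 100 participant-days.

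**Step 4. Check the cross-reference.** Section 8.6.2 relies on Section 8.2 for the meaning of severe hyperglycemia. Section 8.2.2 defines DKA and reportable hyperglycemia and never uses that term, so part of the trigger has no definition.

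**The case against.** The strongest reply is that most trigger events already have 24 hours. They are device-related, and the protocol gives grounds to call them unexpected: 8.7 says that hypoglycemia risk should be no greater than in everyday living, and 1.4.1 says that DKA risk should not rise. Many would also be serious under the medical-judgment limb of 8.1. The 3-day sentence can be read as residual: it would govern the malfunction report, while the adverse event keeps its own clock. Participants are told in 5.3 to contact staff about DKA, severe hypoglycemia and technical issues. In the pilot section, 4.4 has the Medical Monitor adjudicate every DKA and severe hypoglycemia.

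Much of this stands, and it limits how often the gap opens. It does not close it. The 24-hour route still depends on a discretionary classification, 8.5 is silent on precedence, 5.3 informs the site rather than the Coordinating Center, and neither the form review nor the adjudication has a deadline.

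A reader might also draw stronger conclusions that the documents do not support:

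- *That every malfunction, or every severe hypoglycemia or DKA, triggers study-wide suspension.* Section 8.6.2 requires a malfunction that results in the clinical event, and the gates in 4.4 and 5.2 are limited to PLGS-related DKA and malfunction-related severe hypoglycemia.
- *That other participants remain on a suspect device for up to 3 days.* Three days is a filing deadline from investigator awareness. Section 8.6.2 does not make suspension wait for a form, so it could come sooner. It could also come later, because awareness, review and decision are untimed.
- *That 66 to 69 participant-days are the cost of the slower clock.* Only the difference from 24 hours is attributable to it.
- *That Extension Phase users add to the figure.* At that snapshot SAP 11 projects nobody past Period 2, and Appendix A admits only participants who have completed the trial.

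**Conclusion.** Protocol 8.5 and 8.6.2 are not aligned and should be reconciled. The gap is a trigger or gate event judged both non-serious and expected, together with the uncertainty over any event that fits both clauses of 8.5. The report of such an event is due only within 3 days, and direct notice to the Medical Monitor is not assured.

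The size is about 44 to 46 more PLGS participant-days before the report is due, a little under half of the 100 used for the 5.2 gate. That rests on the rough SAP 11 projection, prompt crossover, and both clocks starting at investigator awareness. It measures the difference in deadlines and does not estimate actual exposure. The documents do not show how often such an event would occur. The case for change is that it costs little and lets the existing suspension rule act sooner.

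**What to change.** In Protocol 8.5, put on the existing 24-hour route, regardless of seriousness or expectedness:

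- any device malfunction associated with severe hypoglycemia, DKA or reportable hyperglycemia; and
- any severe hypoglycemia or DKA possibly related to the PLGS system.

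Keep 3 days for all other adverse events and malfunctions. Add the same events to the list in 8.6.2 of what the Medical Monitor is told. Reconcile the term severe hyperglycemia in 8.6.2 with 8.2.2, which does not define it; the choice of definition is for the sponsor. The suspension rule itself is unchanged.

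Expediting every severe hypoglycemia and DKA regardless of arm or relatedness would go further than this problem requires.

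The cost is about one sentence in each of the two sections, using the existing online form, plus a few more expedited reports. SAP 8.3 does not anticipate enough such events for a formal comparison. The change does not time the steps from event to site awareness or from report to decision, so it shortens one interval only.
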